**Table 1 - Major changes in statistical analysis plan**

SAP Version	Approval Date	Changes	Rationale
1.0	04-Feb-2021	Not Applicable	Original version
2.0	Current version	
Add objective "To demonstrate efficacy of dupilumab on both itch as well as skin lesions within the same participant" and multicomponent endpoint (Proportion of participants with both an improvement (reduction) in WI-NRS by <math>\geq 4</math> from baseline to Week 24 and an IGA PN-S 0 or 1 score at Week 24) as a key secondary endpoint for the US and US reference countries hierarchy.
 
Add supplementary analysis (tipping point analyses) for primary and key secondary endpoints
 
Add subgroup analyses for key secondary endpoints.
 
Add subgroup analyses for participants who have been impacted (or not) by COVID-19
 
Modify hierarchical order for multiplicity procedure for US and US reference countries
 
Add as-observed plus multiple imputation supplementary analysis for the secondary endpoint (percent change from baseline in WI-NRS at Week 24)
 
Remove "selected" in the text including "selected prohibited and/or rescue medication"
	
To add this multicomponent endpoint as another measure of treatment success based on feedback from a health authority.
 
This additional supplementary analysis was recommended by a health authority to assess whether the estimate, and the inference thereof, was robust to departure from the strategies used in primary analysis for handling intercurrent events and missing data.
 
To evaluate whether the treatment effect is consistent across pre-specified subgroups on the key secondary endpoints in addition to the primary endpoint.
 
To address a health authority's request to assess the impact of the treatment effect by COVID-19.
 
To include the multicomponent endpoint in the hierarchy to address the health authority's feedback requesting assessment of this endpoint as another measure of treatment success.
 
To explore the robustness of the estimate, and the inference thereof, with a different strategy for handling intercurrent events and missing data
 
Since a participant who takes any protocol specified prohibited medications/procedures and/or rescue

SAP Version	Approval Date	Changes	Rationale
			medications is considered as a non-responder after medical adjudication/confirmation conducted in a blinded fashion, use of the word "selected" is confusing.

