**Table 3 - Summary of primary estimand for main endpoints**

Endpoint Category	Estimands			Population-level summary
	Endpoint(s) a	Population	Intercurrent event(s) strategy and missing data handling	
Primary objective: To demonstrate the efficacy of dupilumab on itch response in participants with PN, inadequately controlled on topical prescription therapies or when those therapies are not advisable.				
Primary endpoint	Proportion of participants with improvement (reduction) in worst-itch numeric rating scale (WI-NRS) by $\geq 4$ from baseline to Week 12	ITT	
The intercurrent events will be handled as follows:
 

• Discontinuation of study treatment before Week 12: Off-study treatment data up to Week 12 will be included in the analysis (treatment policy strategy).

• Taking the prohibited medications/procedures and/or rescue medicationsb prior to Week 12: Participants will be considered as non-responders (composite strategy).

 
In addition, the missing data imputation rules are as follows:
 

• Having missing data at Week 12: Participants will be considered as non-responders.

	CMH test adjusted by documented history of atopy (atopic or non-atopic), stable use of TCS/TCI (yes or no), region (countries combined), and baseline antidepressant use (yes or no).

Endpoint Category	Estimands			Population-level summary
	Endpoint(s) a	Population	Intercurrent event(s) strategy and missing data handling	
Secondary objective: To demonstrate the efficacy of dupilumab on additional itch endpoints in participants with PN, inadequately controlled on topical prescription therapies or when those therapies are not advisable.				

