For any participant randomized more than once, only the data associated with the first randomization will be used in any analysis population. The safety experience associated with any later randomization will be reported separately.

For participants receiving more than one study intervention (placebo and dupilumab) during the study, the intervention group for as-treated analysis will be the dupilumab group.

Regarding the COVID-19 pandemic, additional summaries by COVID-19 subgroups (i.e., impacted by the COVID-19 pandemic and NOT impacted by the COVID-19 pandemic) will be provided to assess the impact of COVID-19 on treatment effect. Participants impacted by the COVID-19 pandemic are defined as randomized participants with any critical or major deviation related to COVID-19 or who permanently discontinued study intervention or study due to COVID-19.

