#### 4.3.5 Subgroup analyses

To assess the homogeneity of the treatment effect across various subgroups, analyses will be performed on the primary endpoint across the following subgroups (categories with fewer than 5 participants may be combined with other categories):

- Age group (<65,  $\geq$ 65 years)
- Gender (Male, Female)
- Region
- Territory
- Race (Caucasian/White, Black/of African descent, Asian/Oriental, Others)
- Ethnicity (Hispanic or Latino, Not Hispanic or Latino)
- Baseline weight (<60,  $\geq$ 60- < 90,  $\geq$  90 kg)
- Baseline BMI (<25,  $\geq$ 25- <30,  $\geq$ 30 kg/m^2)
- Participants without a current diagnosis of AD
- History of atopy (atopic or non-atopic)
- Stable use of TCS/TCI (yes or no)
- Antidepressant use (yes or no) at baseline
- Baseline IGA PN-S moderate versus severe (3 vs. 4)
- Participants who have not been impacted by COVID-19 vs impacted by COVID-19 (for participants who have been impacted by the COVID-19, the efficacy data will be descriptive only if the number of participants is not enough to perform statistical tests. Participants impacted by the COVID-19 pandemic are defined as randomized participants with any critical or major deviation related to COVID-19 or who permanently discontinued study intervention or study due to COVID-19.)

To test the interaction between intervention and subgroup factor, a logistic regression model incorporating subgroup-by-treatment interaction will be built for each subgroup factor except the subgroup of participants without a current diagnosis of AD (very few AD participants will be excluded). The model will include all the covariates in the main statistical model plus the subgroup variable and the subgroup-by-treatment interaction. A p-value for the test of interaction will be provided.

In each subgroup, the treatment effects for the primary endpoint will be provided, as well as the corresponding 95% CI, using the same method as applied to the primary analysis. Forest plots will be provided.

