#### **4.4.1.2 *Main analytical approach***

For the key secondary efficacy endpoints, the analysis will be conducted by using CMH test adjusted by documented history of atopy (atopic or non-atopic), stable use of TCS/TCI (yes or no), region, and baseline anti-depressant use (yes or no). The same estimand, i.e., intercurrent event strategy and missing data handling method, as the primary endpoint, by replacing Week 12 with Week 24, is used.

The same supplementary and subgroup analyses used for the primary endpoint will also be performed for the key secondary efficacy endpoints.

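### The COVID-19 impacted subgroup is formed by post-randomisation events with no time limit, yet is analysed like a baseline factor, so its subgroup differences cannot reliably show whether the pandemic changed the treatment effect

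*SAP*

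**What the plan says.** SAP section 4.3.5 defines impacted participants as randomised participants "with any critical or major deviation related to COVID-19 or who permanently discontinued study intervention or study due to COVID-19". Section 3 gives the same definition and the purpose: the summaries "will be provided to assess the impact of COVID-19 on treatment effect". SAP Table 1 gives the origin: "To address a health authority's request to assess the impact of the treatment effect by COVID-19".

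The factor stands in the same list as age, sex, region, weight, history of atopy and baseline severity. For each factor the section plans a logistic model with a subgroup-by-treatment term ("A p-value for the test of interaction will be provided"), a treatment effect with 95% confidence interval in each subgroup, and forest plots. The one factor excused from the interaction model is absence of a current AD diagnosis. A separate clause makes the impacted group's efficacy data descriptive if there are too few participants to test; it sets no threshold. SAP section 4.4.1.2 carries all of this to Week 24: "The same supplementary and subgroup analyses used for the primary endpoint will also be performed for the key secondary efficacy endpoints".

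For the endpoint itself, SAP Table 3 states: "Having missing data at Week 12: Participants will be considered as non-responders". Stopping study treatment is handled differently there: values collected off treatment are used.

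**The concern.** Every other factor in the list is a baseline or entry characteristic, so randomisation protects the comparison within each level. Here the level can be decided by what happens during follow-up. This has three consequences.

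- Whether someone acquires a major COVID-19 deviation, or gives COVID-19 as the reason for stopping, can depend on arm and on how well the itch is doing.
- There is no time limit. A COVID-19 event in Week 18 labels a participant impacted for the Week 12 endpoint, which it cannot have changed.
- Leaving the study before the endpoint because of COVID-19 places a participant in the impacted group and, through the missing-data rule, makes that participant a non-responder.

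At stake is the answer to a health authority's question. A smaller difference in the impacted group could be read as a pandemic effect on the drug when it comes from imputation or selection. A non-significant interaction could be read as reassurance that it cannot give.

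**Working it through.** **Inputs.** The documents give no expected size for this subgroup, so there is no figure of the plan's own to reproduce. The response rates are blacked out in Protocol 9.2 and SAP section 2. From the plan: about 75 participants per arm, 15% assumed drop-out by Week 12, missing endpoint counted as non-response. Response rates, the impacted share and the missing share *q* within it are assumptions.

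**Step 1: which routes into the group entail non-response?**

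| Route into the impacted group | Consequence under SAP Table 3 |
|---|---|
| Leaves the study because of COVID-19 before the endpoint, endpoint missing | Non-responder by rule |
| Stops study treatment because of COVID-19, stays in follow-up | Observed value used |
| Critical or major COVID-19 deviation only | Not an intercurrent event; observed value used |
| Any COVID-19 event after the endpoint | Cannot affect the endpoint, still labelled impacted |

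WI-NRS is recorded daily in an e-diary and the Week 12 score averages the non-missing days in Days 82 to 88, so a missed visit alone does not empty it. IGA PN-S needs an investigator assessment and is more exposed.

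**Step 2: dilution of the risk difference.** If a share *q* of the impacted group is missing in both arms and counted as non-response, with no effect modification:

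observed difference = (1 − q) × (p_D − p_P)

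- Assumed 45% v 20%, q = 50%: 22.5% − 10% = 12.5 points, against 25.
- Odds ratio: (0.225/0.775) ÷ (0.10/0.90) = 2.6, against (0.45/0.55) ÷ (0.20/0.80) = 3.3.
- Assumed 15% v 43% (28 points, odds ratio 4.27): 21, 14 and 7 points for q = 25%, 50% and 75%. With q = 0 and membership unrelated to arm or outcome, 28 points in both groups.

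These figures depend on *q*, not on how large the impacted group is.

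**Step 3: the interaction test under equal dilution.** In 20,000 simulated trials per scenario (75 per arm; placebo 10–20%, dupilumab 36–49%; 10–30% impacted; q = 50–75%; Wald test, no other covariates; no effect modification) it rejected in 0.3–4.7% of trials. Equal dilution barely moves the p-value. At q = 50%, a zero cell occurred in 11–65% of trials.

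**Step 4: selection.** Assume 15% v 43%, complete data, and that 30% of placebo non-responders but 10% of placebo responders become impacted, against 20% of all dupilumab participants.

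- Placebo impacted share: 0.85 × 0.30 + 0.15 × 0.10 = 0.27. Response among them: 0.015/0.27 = 5.6%. Among the others: 0.135/0.73 = 18.5%.
- Dupilumab stays at 43% in both groups.
- Impacted: 37.4 points, odds ratio 12.8. Not impacted: 24.5 points, odds ratio 3.3. Truth: 28 points, 4.27.

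Even so, the test rejected in only 3.9% of simulated trials (8.6% at 20% v 49%). The estimates are distorted; the p-value gives little sign of it.

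If selection follows response equally in both arms, the effect is small. Take 45% v 20%, with COVID-19 withdrawal probability r in responders and 3r in non-responders, averaging 10%. The pooled response is 32.5%, so (0.325 + 3 × 0.675) r = 2.35 r = 0.10, r = 4.26% and 3r = 12.77%.

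- Not-impacted dupilumab: 0.45 × 0.9574 ÷ (0.45 × 0.9574 + 0.55 × 0.8723) = 47.3%.
- Not-impacted placebo: 0.20 × 0.9574 ÷ (0.20 × 0.9574 + 0.80 × 0.8723) = 21.5%.
- Difference 25.8 points against 25. The odds ratio stays at 3.27, because the factor 0.9574/0.8723 cancels between arms.

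**Step 5: can a null result reassure?** With 15–45 impacted participants and the drug effect wholly lost in them, the test rejected in 5–32% of trials at q = 0 and 1–16% at q = 50%.

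**The case against.** The strongest reply has four parts.

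*Most routes do not make anyone a non-responder.* This stands. A reader might infer that the defining events themselves cause non-response. Table 3 does not support that for treatment discontinuation or for a deviation alone, and the e-diary protects WI-NRS. Even for IGA PN-S, the Week 24 window is wide (Days 127 to 210) and Protocol section 8 allows home visits.

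*The SAP already falls back to description when numbers are small.* This stands in part. The clause has no threshold and addresses sparse data only. It does not address selection after randomisation or events after the endpoint.

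*The hybrid and tipping-point analyses already treat missing data differently.* The hybrid analysis does multiply impute for participants who stop for reasons other than lack of efficacy. But both analyses also change how rescue and prohibited medication is handled, so a shift from the primary result cannot be attributed to COVID-19 missingness. Protocol 9.4.3 names missing data due to COVID-19 as a topic for the SAP, and no efficacy analysis there isolates it.

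*Response lost through withdrawal belongs to the planned estimand.* This is true of the overall estimate. It does not make a contrast between groups defined by that withdrawal a measure of how the drug's effect changed.

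The assumed shares are also open to challenge. A 20% impacted share with half of them missing would mean 10% of all participants lost to COVID-19 by Week 12, against 15% planned drop-out from all causes. Nothing in the documents supports or excludes such a figure.

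**Conclusion.** The point holds as a minor one. The subgroup conditions on events after randomisation without a time limit and is given the inferential treatment of a baseline factor. Its risk differences can be halved with no change in drug effect (12.5 against 25 points at 45% v 20% with half missing), more plausibly for IGA PN-S than for WI-NRS. Arm-dependent selection can pull the subgroup odds ratios apart (12.8 and 3.3 against 4.27). These sizes rest on assumed rates and shares; the absence of a time limit and the missing-data rule are in the text.

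Three stronger readings are not supported. A reader might infer that the analysis can show nothing: if COVID-19 events are unrelated to arm and outcome and data are complete, the within-group comparison is approximately unbiased. A reader might infer false-positive interactions or a clearly inflated effect in the not-impacted group: equal dilution gave at most 4.7% rejections, and selection on response equal in both arms added 0.8 points and left the odds ratio unchanged. A reader might infer damage to the trial's conclusions: the analysis lies outside the hierarchy in SAP section 4.6, so the confirmatory results stand.

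**What to change.** 1. In SAP section 4.3.5, and through 4.4.1.2 for the key secondary endpoints, make the COVID-19 factor descriptive whatever its size, with no interaction p-value and no forest-plot entry.
2. Count only COVID-19 events before the endpoint concerned, and make the same change in section 3.
3. Tabulate impacted participants by arm, type of event (study withdrawal, treatment discontinuation, deviation) and timing, with the number whose endpoint is missing.
4. Add one supplementary run per primary and key secondary endpoint. Keep the primary handling of rescue and prohibited medication. Where the value is missing because of COVID-19, multiply impute it with the approach already planned in section 4.3.4 instead of setting it to non-response. Fix the list of such values before unblinding.

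The cost is SAP wording and one further run of existing code for each of up to four endpoints (the primary, the two key secondary and the combined endpoint for the US hierarchy). IGA PN-S needs its own imputation variables. What is given up is an interaction p-value for this factor. The health authority's request appears only as a one-line rationale, so the sponsor should check the revised wording against the full text.

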## **4.4 SECONDARY ENDPOINT(S) ANALYSIS**

The weekly average skin Pain-NRS or Sleep-NRS score at each week, which is defined as the average of non-missing daily scores within the week window of each week (see [Section 5.4](#)), will be used for analyses.

### **4.4.1 Key/Confirmatory secondary endpoint(s)**

#### **4.4.1.1 *Definition of endpoint(s)***

The key secondary endpoints are:

- Proportion of participants with improvement (reduction) in WI-NRS by  $\geq 4$  from baseline to Week 24, and
- Proportion of participants with IGA PN-S 0 or 1 score at Week 24.

In addition, for US and US reference countries only, there is another key secondary endpoint:

- Proportion of participants with both an improvement (reduction) in WI-NRS by  $\geq 4$  from baseline to Week 24 and an IGA PN-S 0 or 1 score at Week 24.

#### **Investigator's global assessment for prurigo nodularis (IGA PN)**

The IGA PN is a clinician-reported outcome (ClinRO) that allows clinicians to assess the activity of PN (IGA PN-A) using a 5-point scale from 0 (clear) to 4 (severe); and the stage of the disease (IGA PN-S) using a 5-point scale from 0 (clear) to 4 (severe).

#### **4.4.1.2 *Main analytical approach***

For the key secondary efficacy endpoints, the analysis will be conducted by using CMH test adjusted by documented history of atopy (atopic or non-atopic), stable use of TCS/TCI (yes or no), region, and baseline anti-depressant use (yes or no). The same estimand, i.e., intercurrent event strategy and missing data handling method, as the primary endpoint, by replacing Week 12 with Week 24, is used.

The same supplementary and subgroup analyses used for the primary endpoint will also be performed for the key secondary efficacy endpoints.

#### **4.4.2 Supportive secondary endpoint(s)**

The other secondary endpoints are as follows:

- Proportion of participants with WI-NRS reduction  $\geq 4$  over time until Week 24.
- Proportion of participants with WI-NRS reduction  $\geq 4$  at Week 4
- Proportion of participants with IGA PN-S 0 or 1 score at Week 12
- Proportion of participants with IGA PN-S 0 or 1 score at Week 8
- Proportion of participants with IGA PN-S 0 or 1 score at Week 4
- Proportion of participants with IGA PN-A 0 or 1 score at Week 24
- Proportion of participants with IGA PN-A 0 or 1 score at Week 12
- Proportion of participants with IGA PN-A 0 or 1 score at Week 8
- Proportion of participants with IGA PN-A 0 or 1 score at Week 4
- Time to onset of effect on pruritus as measured by proportion of participants with an improvement (reduction) in WI-NRS by  $\geq 4$  from baseline during the 24-week treatment period
- Change from baseline in WI-NRS at Week 24
- Change from baseline in WI-NRS at Week 12
- Percent change from baseline in WI-NRS at Week 24
- Percent change from baseline in WI-NRS at Week 12
- Percent change from baseline in WI-NRS at Week 4
- Percent change from baseline in WI-NRS at Week 2
- Percent change from baseline in WI-NRS over time until Week 24.
- Onset of action in change from baseline in WI-NRS (first  $p < 0.05$  difference from placebo in the daily WI-NRS that remains significant at subsequent measurements) until Week 12
- Change from baseline in IGA PN-S score at Week 24
- Change from baseline in IGA PN-S score at Week 12
- Change from baseline in IGA PN-S score at Week 8
- Change from baseline in IGA PN-S score at Week 4
- Change from baseline in HRQoL, as measured by Dermatology Life Quality Index (DLQI) to Week 24

- Change from baseline in HRQoL, as measured by Dermatology Life Quality Index (DLQI) to Week 12

### Dermatology life quality index (DLQI)

The DLQI is a PRO developed to measure dermatology-specific HRQoL in adult participants. The instrument comprises 10 items assessing the impact of skin disease on participants' HRQoL over the previous week. The items cover symptoms, leisure activities, work/school or holiday time, personal relationships including intimate, the side effects of treatment, and emotional reactions to having a skin disease. It is a validated questionnaire used in clinical practice and clinical trials. Response scale is a 4-point Likert scale (0 = "not at all" and 3 = "very much") for nine items. The remaining one item about work/studying asks whether work/study has been prevented and then (if "No") to what degree the skin condition has been a problem at work/study; the item is rated on a 3-point Likert scale ("Not at all" to "A lot"). Overall scoring ranges from 0 to 30, with a high score indicative of a poor HRQoL.

### ***Time-to-event secondary efficacy endpoint***

Time to first onset of effect on pruritus defined as an improvement (reduction) in WI-NRS by  $\geq 4$  from baseline during the 24-week treatment period will be analyzed using the Cox proportional hazards model, including treatment, documented history of atopy (atopic or non-atopic), stable use of TCS/TCI (yes or no), region, and baseline anti-depressant use (yes or no). The hazards ratio, its 95% confidence interval and p-value will be reported. Kaplan-Meier curves will be also provided.

For time to first WI-NRS response (WI-NRS by  $\geq 4$  from baseline), participants who receive the prohibited medications and/or rescue medications (see [Table 5](#)), data prior to start of the medications will be used, but after medication start, the participants' data will not be used and they will be censored at Week 24 (i.e. Day 172). For other participants, all available data up to Week 24 (i.e. Day 172) including those collected during the off-treatment period will be used. Participants without events will be censored at Day 172 or their last WI-NRS assessment date if discontinued from the study, whichever is earlier.

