Secondary endpoint	Time to onset of effect on pruritus as measured by proportion of participants with an improvement (reduction) in WI-NRS by $\geq 4$ from baseline during the 24-week treatment period	ITT	
The intercurrent events will be handled as follows:
 

Discontinuation of study treatment before Week 24: Off-study treatment data up to Week 24 will be included in the analysis (treatment policy strategy).

Taking the prohibited medications/procedures and/or rescue medicationsb prior to Week 24: Analyses will be censored at Week 24 (composite strategy).

 
In addition, the missing data imputation rules are as follows:
 

Discontinuing the study follow-up before Week 24: Analyses will be censored at the time of last WI-NRS assessment.

	This time-to-event endpoint will be analyzed using the Cox proportional hazards model, including intervention group, documented history of atopy (atopic or non-atopic), stable use of TCS/TCI (yes or no), region (countries combined), and baseline antidepressant use (yes or no). The hazards ratio, its 95% confidence interval and p-value will be reported. Kaplan-Meier curves will be also provided.

Endpoint Category	Estimands			Population-level summary
	Endpoint(s) a	Population	Intercurrent event(s) strategy and missing data handling	

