#### 4.3.2 Main analytical approach

The primary estimand for the primary endpoint is the treatment policy/composite approach as defined in [Table 3](#).

The primary analysis population for the efficacy endpoints will be the ITT population.

The following null hypothesis H0 and alternative hypothesis H1 will be tested for dupilumab against placebo:

- H0: No treatment difference between dupilumab and placebo.
- H1: There is a treatment difference between dupilumab and placebo

The primary analysis will be conducted by using Cochran–Mantel–Haenszel test (CMH) test adjusted by documented history of atopy (atopic or non-atopic), stable use of TCS/TCI (yes or no), region, and baseline anti-depressant use (yes or no). Comparisons of the response rates between dupilumab and placebo will be derived. In addition, odds ratio and response rate difference as well as the corresponding 95% confidence intervals (CI) will be provided along with the p-values.

As defined in [Table 3](#) for participants discontinuing the study treatment before Week 12, their off-study treatment values measured up to Week 12 will be included in the analysis. Participants taking the prohibited medications/procedures and/or rescue medications (see [Table 5](#)) prior to Week 12 or having missing data at Week 12 will be considered non-responders.

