### ***Continuous secondary efficacy endpoints***

The primary estimand for continuous secondary efficacy endpoints is defined in [Table 3](#) and will be analyzed using an analysis of covariance (ANCOVA) model with intervention group, documented history of atopy (atopic or non-atopic), stable use of TCS/TCI (yes or no), region (countries combined), baseline antidepressant use (yes or no), and relevant baseline measurement as covariate, with intercurrent event strategy and missing data handling as defined as in [Table 3](#). Specifically, data of participants taking the prohibited medications/procedures and/or rescue medications will be set to missing after the medication usage, and the worst postbaseline value on

or before the time of the medication usage will be used to impute missing endpoint value (for participants whose postbaseline values are all missing, the baseline will be used to impute). Participants who discontinue the treatment prematurely are encouraged to follow the planned clinical visits and in those participants who did not take the prohibited medications/procedures and/or rescue medications, all data collected after treatment discontinuation will be used in the analysis. For these participants, missing data may still happen despite all efforts have been tried to collect the data after treatment discontinuation. For participants who discontinue due to lack of efficacy, all data collected after discontinuation will be used in the analysis, and a WOCF approach will be used to impute missing data if needed. For participants who discontinued not due to lack of efficacy, a multiple imputation (MI) approach will be used to impute missing endpoint value, and this MI method will use all participants excluding participants who have taken the prohibited medications/procedures and/or rescue medications prior to timepoint of endpoint of interest and excluding participants who discontinue due to lack of efficacy.

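### The supportive time-to-first-response analysis censors every event-free study leaver at the last itch score, so those who leave for lack of efficacy without rescue are assumed to respond later like those who stay (low severity)

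*SAP*

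**What the plan says.** SAP Section 4.4.2 (time-to-event endpoint) fits a Cox model and Kaplan-Meier curves to the time to the first WI-NRS reduction of at least 4 within 24 weeks. The censoring rule is "Participants without events will be censored at Day 172 or their last WI-NRS assessment date if discontinued from the study, whichever is earlier". The estimand table (SAP Table 3) agrees: "Discontinuing the study follow-up before Week 24: Analyses will be censored at the time of last WI-NRS assessment". Neither place makes an exception by reason for leaving.

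Three neighbouring rules matter.

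- **Rescue or prohibited medication, same endpoint.** After the medication starts, "the participants' data will not be used and they will be censored at Week 24 (i.e. Day 172"). Table 3 labels this a composite strategy.
- **Stopping treatment only, same endpoint.** For participants without such medication, all scores to Day 172, "including those collected during the off-treatment period will be used". Stopping treatment therefore does not censor; leaving the study does.
- **Lack of efficacy, continuous endpoints.** "For participants who discontinue due to lack of efficacy, all data collected after discontinuation will be used in the analysis, and a WOCF approach" fills what is missing. These participants are also left out of the multiple imputation.

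For responder endpoints, participants "having missing data at Week 12 will be considered non-responders", whatever the reason. SAP Section 4.4.1.2 carries this to Week 24. The SAP states no sensitivity or supplementary analysis of the time-to-event censoring rule.

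**The concern.** Cox and Kaplan-Meier need censoring to be unrelated to later response, given the model's covariates. Leaving because the treatment does not work is related to it. Under the planned rule such a participant drops out of the risk set and is implicitly given the later response rate of those who remain.

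The plan avoids this for failures that show themselves in another way. A failing participant who takes rescue stays in the risk set as a non-event to Day 172; one who simply leaves does not. In the continuous analysis the sponsor keeps lack-of-efficacy discontinuers out of the imputation model, which is a statement that they are not exchangeable with those who stay.

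At stake are the reported hazard ratio, its confidence interval and p-value, and the Kaplan-Meier curves for this endpoint.

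**Working it through.** **Inputs.** 75 participants per arm (SAP Section 1.1). Dropout of 15% over 12 weeks (SAP Section 2), not split by reason and with no Week 24 figure. Response rates are redacted. No event count, hazard ratio (HR) or power is given for this endpoint, so there is no plan figure to reproduce. The censoring day is consistent: the Week 24 target day is 24 × 7 + 1 = 169, and 169 + 3 = 172, the end of the Week 24 diary window in SAP Table 10.

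Pairs below are dupilumab/placebo. All response rates and exit shares are assumptions.

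**Mechanism.** Let r be the true share responding by Week 24 and l the share who never respond and leave. If all of them left before the first response, the Kaplan-Meier estimate would be r/(1 − l). With r = 60%/30% and l = 10% in each arm:

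- dupilumab: 0.60/0.90 = 66.7%
- placebo: 0.30/0.90 = 33.3%

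The true values are 60% and 30%. Later exits inflate the curves less. Equal exits push the HR away from 1 because the dupilumab arm has fewer event-free participants, so the same number of exits is a larger share of its risk set.

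**Simulation at trial size.** 75 per arm, 600 runs, unadjusted Cox model, true response 60%/30%. Responses are spread evenly over Days 8–172. Leavers are never-responders who exit evenly over Days 28–140. The shift in log HR is ln(planned)/ln(Day 172) − 1.

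| Exits, dupilumab/placebo | HR planned | HR with Day 172 | Shift in log HR | Kaplan-Meier planned | Kaplan-Meier with Day 172 |
|---|---|---|---|---|---|
| 0%/0% | 2.59 | 2.59 | 0 | 60.6%/29.8% | 60.6%/29.8% |
| 2%/5% | 2.48 | 2.53 | 0.908/0.928 − 1 = −2% | 60.3%/30.8% | 59.5%/29.8% |
| 3%/10% | 2.44 | 2.55 | 0.892/0.936 − 1 = −5% | 61.4%/31.8% | 60.1%/29.8% |
| 5%/20% | 2.30 | 2.56 | 0.833/0.940 − 1 = −11% | 62.6%/34.4% | 60.3%/29.9% |
| 10%/10% | 2.63 | 2.54 | 0.967/0.932 − 1 = +4% | 65.4%/32.3% | 60.5%/30.3% |
| 10%/3% | 2.78 | 2.54 | 1.022/0.932 − 1 = +10% | 65.2%/30.7% | 60.3%/30.1% |

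With response 50%/20% the pattern is the same. For example, 5%/20% exits give 2.81 planned against 3.11.

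**Large-sample simulation.** Response 60%/30%, 50%/20% or 40%/12%, earlier in the period than above. Leavers are all never-responders who exit over Weeks 1–12.

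- Exits 15%/15%: log HR overstated by about 2–5.5%; Week 24 Kaplan-Meier difference overstated by 11–14% (at 60%/30%, 0.302 becomes 0.344, and 0.344/0.302 = 1.14).
- Exits 10%/20%: log HR reduced by about 3–5%.
- Exits 5%/25%: log HR reduced by about 8–15% (one run: HR 2.49 becomes 2.19, and 0.784/0.912 − 1 = −14%).
- Exits 2%/5%: log HR reduced by about 0.5–1.5%. With the −2% from the table above, I quote 0.5–2%.

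**Against sampling error.** At 60%/30% the expected events are 75 × 0.60 = 45 and 75 × 0.30 = 22.5. The standard error of the log HR is about √(1/45 + 1/22.5) = 0.26. The 2%/5% case shifts it by 0.928 − 0.908 = 0.020, under 0.1 standard errors. The 5%/25% case shifts it by 0.912 − 0.784 = 0.128, about 0.5 standard errors.

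**The case against.** The strongest reply is that few participants can be affected. They must be event-free, leave the study and not just treatment, have taken no rescue or prohibited medication first, and have left for lack of efficacy. Rescue is available throughout (Protocol Section 6.5.1) and already triggers the Day 172 rule. Treatment discontinuers are asked to complete all visits (Protocol Section 7.1.1), and study withdrawal is expected to be uncommon (Protocol Section 7.2). This stands, and it is why the larger figures above are upper bounds. It does not remove the inconsistency, because the rule is explicit and nothing tests it.

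Two further points stand. The SAP sets missing-data handling by endpoint type, and its responder and continuous rules already differ from each other, so some difference is by design. And the continuous rule is triggered by the reason for stopping treatment, while this censoring is triggered by leaving the study. The named grounds for study withdrawal in Protocol Section 7.2 do not include lack of efficacy, so a failure may be recorded as the participant's own request. The fix has to allow for that.

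A reader might also infer that the Week 24 Kaplan-Meier proportions would contradict the Week 24 responder analysis because of this rule. The documents do not support that as evidence. One endpoint counts the first response by Week 24 and the other the status at Week 24, so they can differ under any censoring rule.

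**Conclusion.** The point holds at low severity. The planned rule treats lack-of-efficacy exits without rescue as uninformative, whereas the same endpoint's rescue rule and the continuous analysis treat failures as not exchangeable with those who stay.

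The direction is not fixed. The HR moves toward 1 if these exits are mainly on placebo, and away from 1 if they are about equal or mainly on dupilumab. The Kaplan-Meier curve is inflated in any arm that loses such participants. A reader might infer that the rule favours dupilumab; nothing in the documents gives the split by arm that this would need.

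The size rests on assumed response rates and exit shares: about 0.5–2% of the log HR with exits of 2%/5%, and up to about 8–15% if exits are 5%/25% and all early. A reader might apply the plan's 15% dropout in full, but that figure covers all reasons, so doing so gives an upper bound.

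A reader might also infer that the trial's conclusions are at risk. They are not: this endpoint is in neither testing hierarchy of SAP Section 4.6, so the primary and key secondary results and the type I error are unaffected.

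**What to change.** Before unblinding, state in SAP Section 4.4.2 and the time-to-onset row of Table 3 that an event-free participant who leaves the study is censored at Day 172 if the recorded reason for permanent treatment discontinuation, or for study discontinuation where given, is lack of efficacy. This is the existing rule for rescue or prohibited medication. Keep censoring at the last WI-NRS assessment for other reasons. The same sentence can confirm that a participant who takes rescue and then leaves follows the Day 172 rule, as Table 3 implies.

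Add one supplementary run that carries all event-free study leavers to Day 172, because some failures may be recorded under another reason.

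The cost is a sentence in each place, a line of derivation code and one extra run. Reasons for both kinds of discontinuation are already collected and tabulated (Protocol Section 7, SAP Section 4.2). The downsides are slightly lower curves and dependence on the recorded reason, which the continuous analysis already accepts.
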